**Directional Lead: Investigation of Rotational Current Steering, Ease of Use
of Clinical Effects Map, and Therapeutic Outcomes of Deep Brain
Stimulation**

DIRECT-DBS

CLINICAL INVESTIGATION PLAN

Sponsored By

Boston Scientific Corporation
Neuromodulation
[name]
[name]
United States of America

International Representative

Boston Scientific Limited
[name],
Galway, Ireland

This protocol contains confidential information for use by the Investigators and their designated representatives participating in this clinical investigation. The protocol should be held confidential and maintained in a secure location.

Do not copy or distribute without written permission from Boston Scientific Corporation.

THESE DOCUMENTS ARE THE PROPERTY OF BOSTON SCIENTIFIC CORP. AND SHALL NOT BE REPRODUCED, DISTRIBUTED, DISCLOSED OR USED FOR MANUFACTURE OR SALE OF APPARATUS WITHOUT THE EXPRESS WRITTEN CONSENT OF BOSTON SCIENTIFIC CORP.

Boston Scientific
DIRECT-DBS Study-Specific Protocol

Contact Information

Role	Contact
Clinical Contact	[name] Director International Clinical Operations Boston Scientific Corporation [name] Netherlands [name] [contact]
Coordinating Principal Investigator	[name] Neurologische Klinik und Poliklinik Universitätsklinikum Würzburg [name] GERMANY
Coordinating Co-Principal Investigator	[name] Clinique de Neurochirurgie, Pôle TCCR CHU MICHALLON, [name] France

[REDACTED]
[REDACTED]
[REDACTED]

[REDACTED]	[REDACTED]	[REDACTED]	[REDACTED]	[REDACTED]	[REDACTED]
[REDACTED]	[REDACTED]	[REDACTED]	[REDACTED]	[REDACTED]	[REDACTED]
[REDACTED]	[REDACTED]	[REDACTED]	[REDACTED]	[REDACTED]	[REDACTED]
AB	25Feb2016	90702637 Rev./Ver. AF	11.6	[REDACTED]	[REDACTED]

2. Protocol Synopsis

Directional Lead: Investigation of Rotational Current Steering, Ease of Use of Clinical Effects Map, and Therapeutic Outcomes of Deep Brain Stimulation
 
DIRECT-DBS STUDY
	

Study Objective(s)
	
The primary objective is to characterize the programming effects of Boston Scientific Vercise™ PC System using the DBS Directional Lead for bilateral STN DBS for the treatment of Parkinson’s disease in acute and chronic settings.
 
[REDACTED]

Test Device
	
Boston Scientific Neuromodulation (BSN) Vercise™ PC System with BSN Directional Lead


Control Device
	
None; each patient will serve as their own control

Study Design
	
Prospective, multi-center, open label study with double-blinded exploratory and crossover phases

Planned Number of Patients
	
Up to 12 randomized patients

Planned Number of Investigational Sites / Countries
	
Up to 4 sites in the EU

Primary Endpoint
	
Collected data will be used to guide product development and to build early experience to define the best practice for programming

[REDACTED]
	
[REDACTED]

Directional Lead: Investigation of Rotational Current Steering, Ease of Use of Clinical Effects Map, and Therapeutic Outcomes of Deep Brain Stimulation DIRECT-DBS STUDY
	
	
[REDACTED]
 
[REDACTED]
 
[REDACTED]
 
[REDACTED]
 
[REDACTED]

Method of Assigning Patients to Treatment
	
Eligible patients who consent to participation and have met all of the inclusion and none of the exclusion criteria will undergo implant and intraoperative testing. After 3 months of omnidirectional (Ring Mode) stimulation, the patient will undergo 3 Programming Visits. Patients are then randomized in an equal distribution to best Ring Mode settings or best Unrestricted settings for 4 weeks, followed by crossover to the opposite programming method for 4 additional weeks. After this, patients are followed up to one year post implant where programming can be further optimized

Follow-up Schedule
	
 • Screening (prior to implant) • Implant • 3 Programming Visits (up to 7 days prior to Randomization Visit) • Randomization Visit (90 ± 30 days post first lead placement) • Crossover Visit (28 ± 7 days post Randomization Visit) • Release Visit (56 ± 7 days post Randomization Visit) • 1-Year Follow Up Visit (365 ± 30 days post first lead placement) 
The overall study will be considered complete when the last patient not lost to follow up completes the 1 Year Follow Up Visit

Directional Lead: Investigation of Rotational Current Steering, Ease of Use of Clinical Effects Map, and Therapeutic Outcomes of Deep Brain Stimulation
 
DIRECT-DBS STUDY
	
Study Duration	
The entire study will take less than 2 years to complete.
 
Each patient will be enrolled for approximately 1 year.

Key Inclusion Criteria	
IC1. Candidate for Vercise™ PC DBS with bilateral implant of BSN DBS Directional Leads in STN, and meets:
 
 • Diagnosis of bilateral idiopathic PD with the presence of rigidity and at least one (1) of the following: resting tremor or bradykinesia. • UPDRS III score of >25 in the meds OFF condition • Medication must improve PD symptoms by ≥30%, as measured by UPDRS subset III score 
[REDACTED]
 
IC4. [REDACTED]

Key Exclusion Criteria	
EC1. Any significant psychiatric problems, including unrelated clinically significant depression as determined by the investigator
 
EC2. Any current drug or alcohol abuse as determined by the investigator
 
EC3. Any history of recurrent or unprovoked seizures
 
EC4. Any significant medical condition that is likely to interfere with study procedures or likely to confound evaluation of study endpoints, including any terminal illness with survival <12 months

Statistical Methods	
Primary Statistical Hypothesis	NONE
Statistical Test Method	Descriptive statistics will be employed in post-hoc analysis

Directional Lead: Investigation of Rotational Current Steering, Ease of Use of Clinical Effects Map, and Therapeutic Outcomes of Deep Brain Stimulation
 
DIRECT-DBS STUDY
	
Sample Size Parameters	Sample size not determined in prospective manner

3. Table of Contents

2. PROTOCOL SYNOPSIS.....4

3. TABLE OF CONTENTS.....7

3.1. Table of Figures.....10

3.2. Table of Tables

Table 9.2-1: Inclusion Criteria..... 16

Table 9.3-1: Exclusion Criteria..... 16

Table 11.1-1: Data Collection Schedule 18

Table 11.12-1: Source Documentation Requirements 23

Table 20.2-1: Safety Definitions..... 33

Table 20.3-1: Criteria for Assessing Relationship of Study Device or Procedure to Adverse Event 37

Table 20.4-1: Investigator Reporting Requirements..... 39

Table 27.1-1: Abbreviations 47

Table 27.2-1: Definitions 48

4. Introduction

Parkinson’s disease (PD) is a progressive neurodegenerative disorder that affects 2.0 million Europeans (1). The prevalence of PD is estimated at 0.3% of the overall population in industrialized countries and advances to 1% by age 60 and 4% in the highest age groups (2). The hallmark signs of PD include movement disorders such as bradykinesia, resting tremors, and muscle rigidity (3).

The motor symptoms of PD are associated with a dopamine deficiency resulting from the degradation of dopaminergic neurons in the substantia nigra pars compacta. At present there is no cure for PD; treatment is focused on medical management of motor symptoms. Medical therapy has been primarily focused on restoring dopamine levels through the administration of levodopa, dopamine agonists, or monoamine oxidase B inhibitors. Current standards for patient care recommend levodopa as first line therapy for the symptomatic control during the early, uncomplicated stages of PD (4, 5). Unfortunately, chronic treatment with levodopa frequently leads to significant side effects, especially dyskinesias and motor fluctuations (6).

Previously, for patients who had reduced response to medical therapy, pallidotomy (destruction of the globus pallidus) and thalamotomy (destruction of the thalamus) were the only available surgical treatment options. In the 1990s, high-frequency deep brain stimulation (DBS) was demonstrated to be effective in reducing the motor complications of patients with PD (7). Since that time numerous case studies and trials have substantiated these early findings. In addition, three recent large, multicenter, randomized trials have demonstrated the efficacy of the therapy (8-10). Currently, DBS of the subthalamic nuclei (STN) is recommended as a therapeutic option for appropriate PD patients (5, 11).

This study will compare various program settings for the bilateral stimulation of the STN using the BSC implantable Vercise™ PC DBS System for the treatment of levodopa-responsive, moderate to severe idiopathic PD. The Vercise™ PC System is capable of delivering stimulation similar to other commercially available DBS systems.

[REDACTED]

5. Device Description

The Boston Scientific Vercise™ DBS System received CE mark approval in September 2012 for treatment of Parkinson's disease, in September 2013 for treatment of intractable primary and secondary dystonia and in July 2014 for Essential Tremor. The directional lead, Vercise™ PC system and programming system received CE mark in September 2015

The implantable portion of the Vercise™ PC System includes leads for bilateral stimulation and extensions that allow the leads to be extended to reach the Implantable Pulse Generator (IPG) near the clavicle. The electrode array is placed into the brain, typically targeting the subthalamic nucleus (STN) or Globus Pallidus (GPi). The directional leads can provide stimulation in a ring mode (equally around the lead) or in a directional mode (away from the center of the lead). Once the leads are placed, they are typically secured using physician's standard lead fixation technique. A SureTek™ Burr Hole Cover may be used. Since the leads are often placed under the scalp for some time before being connected to lead extensions or IPG, lead boots will be provided to cover the proximal ends of the leads during this period.

Surgical tools for the Vercise™ PC System include a tunneler. A lead stop (which may be attached to the lead to allow the lead to be located at the appropriate depth in the tissue during its initial placement) will also be provided.

External devices including a Clinician Programmer, programming wand and Remote Control will also be provided for patient/physician use. During implant, the positioning of the lead(s) may be checked using macrostimulation provided by a Vercise™ PC External Trial Stimulator (ETS).

A copy of the device labeling and DFU will be provided in local language(s) as required per national regulations.

5.1. Medical Equipment Description

Kinesia ONE

Commercial, tablet-based system created by Great Lakes NeuroTech (GLNT) which assesses tremor, bradykinesia, hypokinesia, and dysrhythmia in an automated fashion via a patient-worn, finger mounted motion sensor.

Kinesia 360

Commercial tablet-based motor diary system created by Great Lakes NeuroTech (GLNT) which assesses tremor, dyskinesia and mobility during the day in an automated fashion via patient-worn sensors and a mobile app to continuously measure Parkinson's disease.

The Kinesia ONE system is used in the hospital environment while the Kinesia 360 system is used by the patient at home.

6. Study Objectives

The primary objective of this exploratory study is to characterize the programming effects of Boston Scientific Vercise™ PC System using the DBS Directional Lead for bilateral STN DBS for the treatment of Parkinson’s disease in an acute and chronic setting.

[REDACTED]

[REDACTED]

[REDACTED]

[REDACTED]

[REDACTED]

[REDACTED]

[REDACTED]

[REDACTED]

[REDACTED]

8. Study Design

Prospective, multi-center, open label, study with double-blinded exploratory and crossover phases.

[REDACTED]

[REDACTED]

[figure not shown]

Figure 8.1-1: DIRECT-DBS Study Design

8.2. Treatment Assignment

Eligible patients who consent to participation and have met all of the inclusion and none of the exclusion criteria will undergo implant and intraoperative testing. After 3 months of omnidirectional (Ring Mode) stimulation, the patient will undergo 3 Programming Visits. Patients are then randomized in an equal distribution to best Ring Mode settings or best Unrestricted settings for 4 weeks, followed by crossover to the opposite programming method for 4 additional weeks. After this, patient is followed up to one year post implant where programming can be further optimized.

8.2.1. Treatment and Control

Each patient will serve as their own control during Crossover Phase. Symptom comparisons will be made across time and across different stimulation settings.

8.3. *Justification for the Study Design*

The study design is a prospective, multi-center, open label, study with double-blinded exploratory phase and un-blinded crossover phase with a blinded evaluator, characterizing the programming effects of Boston Scientific Vercise™ PC System using the DBS Directional Lead for bilateral STN DBS for the treatment of Parkinson's disease in an acute and chronic setting.

A multi-center design will minimize the impact on treatment outcome that may potentially result from differences in patient selection, regional differences in the patient demographic, and differences in investigator technique and patient management.

The study will include multiple instances of randomization, where the patient will receive stimulation parameters from a preset list in a random order. Randomization will minimize bias due to order of presentation of stimulation settings. A double blind (patient and neurologist assessor) will minimize bias that might impact subjective outcome measures. The programmer will remain un-blinded to provide appropriate care for each patient's programming variables.

The crossover phase requires that the patient is programmed with each of Ring Mode and Unrestricted programming settings for an equal amount of time, in a random order. In this way, patients can each serve as their own control. In order to minimize bias that might impact subjective outcome measures, the physician responsible for evaluating these arms will be blinded.

9. Patient Selection

9.1. *Study Population and Eligibility*

Up to 12 randomized patients may be included in the study.

Patients will generally be recruited from physician's practice and will be eligible to receive Deep Brain Stimulation to treat their Parkinson disease using the commercially-approved BSC Vercise™ PC System per local DFU.

9.2. *Inclusion Criteria*

Patients who meet all of the following criteria (see **Error! Reference source not found.**) may be given consideration for inclusion in this clinical investigation, provided no exclusion criterion (see Section 9.3) is met.

Table 9.2-1: Inclusion Criteria


Clinical Inclusion Criteria
	
IC1. Candidate for Vercise™ PC DBS with bilateral implant of BSN DBS Directional Leads in STN, and meets:
 
 • Diagnosis of bilateral idiopathic PD with the presence of rigidity and at least one (1) of the following: resting tremor or bradykinesia. • UPDRS III score of >25 in the meds OFF condition • Medication must improve PD symptoms by ≥30%, as measured by UPDRS subset III score. 
[REDACTED]
 
[REDACTED]
 
[REDACTED]

---	--

9.3. Exclusion Criteria

Patients who meet any one of the following criteria (**Error! Reference source not found.**) will be excluded from this clinical study.

Table 9.3-1: Exclusion Criteria

Clinical Exclusion Criteria
	
EC1. Any significant psychiatric problems, including unrelated clinically significant depression as determined by the investigator.
 
EC2. Any current drug or alcohol abuse as determined by the investigator.
 
EC3. Any history of recurrent or unprovoked seizures.
 
EC4. Any significant medical condition that is likely to interfere with study procedures or likely to confound evaluation of study endpoints, including any terminal illness with survival <12 months.

---	---

10. Patient Accountability

10.1. Point of Enrollment

A patient will be considered enrolled in this study after he/she signs and dates the informed consent form (ICF). No study-related procedures or assessments can take place until the informed consent form is signed.

10.2. Withdrawal

All patients enrolled in the clinical study (including those withdrawn from the clinical study or lost to follow-up) shall be accounted for and documented. If a patient withdraws from the clinical investigation, the reason(s) shall be reported. If such withdrawal is due to problems related to investigational device safety or performance, the investigator shall ask for the patient’s permission to follow his/her status/condition outside of the clinical study.

Reasons for withdrawal could include but are not limited to

- physician discretion,
- patient choice to withdraw consent; in case of patients under the age of 18 years old, parent/guardian choice to withdraw consent will be considered a valid reason for withdrawal.
- patient's failure to meet inclusion or not meet exclusion criteria after enrollment but prior to system implant,
- failure to receive a BSC DBS system,
- lost to follow-up, or
- death.

While study withdrawal is discouraged, patients may withdraw from the study at any time, with or without reason, and without prejudice to further treatment.

All applicable case report forms (CRFs) up to the point of patient withdrawal and an "End of Study" form must be completed. Any patient deemed "lost to follow-up" should have a minimum of three documented attempts to contact him/her prior to completion of the "End of Study" form.

Additional data may no longer be collected after the point at which a patient has been withdrawn from the study or withdraws consent, for whatever reason. All open adverse events should be closed or documented as unresolved. Data collected up to the point of patient withdrawal may be used and analyzed.

Patients withdrawn after completing the implant procedure will be replaced and will not be included in the site's overall total for randomized patients.

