19.8. Risk to Benefit Rationale

The purpose of this study is to compile characteristics of real-world outcomes for Boston Scientific Corporation's commercially approved Vercise™ PC System for DBS, when used according to the applicable Directions for Use. The mechanism of action of the Vercise™ PC System is the same as other commercially available DBS systems. Based on the clinical data for BSC's approved Vercise™ DBS system, Medtronic's approved Activa DBS System, and St Jude's approved Infinity DBS system, the risk-to-benefit ratio for BSC Vercise™ DBS System is within reason for foreseeable risks. However, studies do not always predict all

side effects that may be experienced. Observation and follow-up of all patients is required as outlined in the protocol.

20. Safety Reporting

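### Section 10.2 stops study data collection at every withdrawal, so safety events in implanted patients who leave without withdrawing consent have no stated route into the study record

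*Combined protocol and SAP*

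**What the plan says.** Section 10.2 (Withdrawal) contains four provisions that matter here.

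- **Bar on data.** "Additional data may no longer be collected after the point at which a patient has been withdrawn from the study". The sentence puts leaving the study and withdrawing consent under one rule: it applies to a patient "withdrawn from the study or withdraws consent, for whatever reason". Physician discretion is one of the listed reasons.
- **Open events.** "All open adverse events should be closed or documented as unresolved".
- **Device-related withdrawals.** "If such withdrawal is due to problems related to investigational device safety or performance", then "the investigator shall ask for the patient’s permission to follow his/her status/condition outside of the clinical study".
- **Accounting.** All enrolled patients, "including those withdrawn from the clinical study or lost to follow-up) shall be accounted for and documented". Forms are completed up to the point of withdrawal, and data to that point may be analysed.

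Section 20.4 requires the investigator to report serious adverse events, device effects and device deficiencies from consent until the patient's participation ends. Section 22.1 has the Medical Director evaluate safety events, working from data collected as events are reported.

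**The concern.** When a patient withdraws consent, a halt to new data respects that decision. When the physician ends participation, or the patient leaves for a reason that does not include refusing further contact, nothing in the documents explains why safety data must stop too. An implanted patient may still carry the system, and may still have an unresolved event when participation ends.

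At stake is how complete the safety record is for patients who leave after implant. Their later serious events, device- or procedure-related events and device deficiencies, and the final outcome of events already open, would be absent from the study data and from the review in 22.1. Section 10.2 also has patients withdrawn after implant replaced, so the number of completed records can be restored while the departed patient's safety record stays cut short.

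**Working it through.** **1. Where the bar bites.** Section 10.2 lists six reasons and says the list is not exhaustive.

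- Two arise without or before an implant: eligibility failure found before implant, and not receiving the system.
- Two leave little or nothing to collect: loss to follow-up and death.
- One is withdrawal of consent, where a bar is appropriate.
- That leaves physician discretion and any unlisted reason. In these cases safety data could still be collected with permission, and the rule forbids it.

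**2. The provisions traced for an implanted patient.**

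| Situation | Later follow-up under 10.2 | Stated route to CRF or sponsor review |
|---|---|---|
| Consent withdrawn, no device reason | None | None; appropriate |
| Leaves because of device safety or performance | Permission sought, outside the study | None |
| Leaves for another reason, e.g. physician discretion after a surgical complication | None | None |

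In the second row there is follow-up but no route. It sits outside the study, 10.2 bars additional data, and the window in 20.4 has closed. Section 22.1 works from reported events and adds no other path.

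In the third row even the outside follow-up is missing. Section 20.3 classes surgical-procedure events separately from hardware and stimulation events, so a surgical complication is not clearly a device safety or performance problem. The permission sentence also follows from a patient who withdraws, whereas the bar extends to one who has been withdrawn. Whether a physician-initiated withdrawal triggers the request for permission is therefore unclear.

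**3. Observation time lost, by example.** The inputs are the Randomization Visit at 90 ± 30 days and the 1-year visit at a nominal 365 days, both counted from first lead placement (Sections 11.7 and 11.10).

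- Earliest Randomization Visit: 90 − 30 = day 60. Time lost: 365 − 60 = 305 days (305/365 = 84%).
- Latest Randomization Visit: 90 + 30 = day 120. Time lost: 365 − 120 = 245 days (245/365 = 67%).

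These are losses for one patient withdrawn at that visit. The documents give no withdrawal rate, so no expected loss for the study can be calculated.

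**The case against.** The strongest reply is that the plan does not abandon these patients. Section 10.2 has the investigator seek permission for continued follow-up in the device case. Section 17.2 obliges the investigator to provide medical care for adverse events after participation as well as during it. Section 19.6 lets the physician halt or reduce testing that poses a greater risk, so a patient with a complication may be protected without being withdrawn. The study is exploratory and descriptive, and it uses a commercially available system. The consent form and parts of the protocol cannot be seen, and they may contain terms on follow-up after withdrawal.

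Most of this stands, and it limits the point. It does not answer it: care and outside follow-up are not data collection, and no visible text connects them to the CRF or to the sponsor.

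A reader might also infer several stronger things that the documents do not support:

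- **That such patients simply drop out of follow-up.** They leave the study's data collection; 10.2 and 17.2 provide for something beyond it.
- **That 19.8 contradicts 10.2.** Section 19.8 says "Observation and follow-up of all patients is required", but the sentence goes on to refer to what the protocol lays out, which includes 10.2.
- **That each case is one twelfth of the cohort.** Twelve is the cap on randomized patients. Those withdrawn after implant are replaced and not counted in the site's randomized total, so the number implanted may be larger.
- **That a safety rate is biased by a known amount.** No visible safety endpoint or rate exists to which a bias could be attached, and the mix of withdrawal reasons is unknown.
- **That the sponsor can withdraw individual patients under this rule, or that the device always remains implanted.** The first is not among the listed reasons. The second is an assumption.

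**Conclusion.** The point holds as a shortcoming in data collection that should be corrected. Sections 10.2 and 20.4 together mean that, if the plan is followed exactly, safety events and event outcomes after a post-implant withdrawal are not captured, even when the patient has not withdrawn consent. The outside follow-up covers only withdrawals for device safety or performance and has no stated reporting route.

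For a patient withdrawn at the Randomization Visit, 245 to 305 planned days of safety observation are lost. That figure assumes withdrawal at that visit and a nominal 1-year visit at day 365. How often this would occur cannot be judged from the documents. The conclusion also assumes that the removed consent form and redacted text do not already settle the matter. It does not threaten the study's descriptive objective on programming effects.

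**What to change.** Split the rule in 10.2.

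- **Consent withdrawn:** collect no new data beyond what the patient permits.
- **Implanted patient withdrawn for any other reason:** with the patient's permission, keep recording serious adverse events, device- and procedure-related adverse events, device deficiencies and the outcome of open related events on the CRF up to the planned 1-year date. State that the follow-up already provided for in device-related withdrawals is recorded in the same way.

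Align the reporting window in 20.4, so that these events reach the sponsor and the review in 22.1.

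The cost is one revised paragraph in 10.2, a matching change in 20.4, a line in the consent form, and a few chart or telephone updates for any patient concerned. No visits or procedures are added, and clinical management does not change.
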